The intervention consists of two parts, Options Counseling (OC) and Health Education (HE). The OC part includes family assessment, counseling and provision of emotional support, access assistance, and development of independent-living plans (care plans) using the Iowa's Heritage Area Agency on Aging database. The Options Counselor is trained to use motivational interviewing techniques to develop family care plans, provide emotional support, and connect families to available services and programs in the community. The HE part includes post-diagnosis family education using the 7-module health education toolkit developed specifically for this study based on the literature and expert reviews. OC-HE will conduct initial assessment to determine educational needs within 2 weeks of participant's randomization into the intervention group and develop initial care plan; and will conduct 5 monthly follow-up calls to adjust the care plan and provide educational components appropriate at each point. This intervention aims to create direct links between the medical clinics, home and community-based services (HCBS), and family.

Participants assigned to the usual care control group will participate in baseline, as well as 3- and 6-months

follow-up surveys. Those in usual care group will receive a general informational brochure from the Alzheimer's Association, and will be given an option of receiving a call from their local Options Counselor after completing the 6-month survey.

Study duration is about 18 months. We aim to start participant enrollment in August, 2019, complete recruitment by September, 2020, and complete data collection by March 2021. Each participant will be enrolled in this study for about 6 months from enrollment to final interview.

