5.0 Recruitment and Retention

Sample

Between June 2015 and May 2016, the 3 UIHC clinics served about 17,500 people with dementia and 657 were newly diagnosed. Power calculations were performed under the assumption of reaching about 12% of newly diagnosed individuals, 106 people; assuming a 25% attrition rate, this will lead to 80 people (40 per group). This will give us about 84% power to detect a 4-point decrease in Caregiving Burden at each 3-month period. Assuming some people may not meet the inclusion criteria, we anticipate screening around 138 potential participants including women and minorities to reach target enrollment size.

Participants

Family participants/caregivers will be family members or friends (e.g., biological and non-biological relatives, friends) who likely will coordinate care and support for the individual who received dementia diagnosis at one of the three participating clinics: Memory Disorder Clinic (Neurology), Geriatric Medicine Clinic (Family Medicine), and Adult Psychiatry (Psychiatry) at the University of Iowa Hospitals and Clinics (UIHC). Potential family participants/caregivers will be referred by the clinical care team members by reviewing EMR in EPIC and identifying patients who have been diagnosed with Alzheimer's or other dementia within the past 6 months. All participants will be asked to participate in a baseline survey and follow-up surveys at three and six months regarding their sociodemographic characteristics, Home and Community-Based Services (HCBS) use and knowledge, caregiving self-efficacy, caregiving preparedness, social support and networks, and their physical and psychological well-being. After completing the baseline, participants will be randomized into either the Options Counselor-Health Educator (OC-HE) intervention group or the standard care (control) group. Participants in the OC-HE intervention group will receive intervention after completing the baseline survey. All consents and interviews will be conducted by the trained research staff from the University of Iowa. Prior to enrolling

participants for the randomized trial, three to five individuals who have family members with dementia diagnosis will be asked to help with pilot testing program materials by providing feedback on the program contents and implementation procedures.

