Research staff and the OC-HE will make up to 3 phone calls, at least three days apart, leaving a message if possible to schedule each encounter. On the 3rd phone call, the research staff or OC-HE will let the participant know that they are welcome to contact the research team if they would like to stay enrolled in the study. The participant will have up to 1 month to call back after the 3rd phone call before they are dropped from the study. To facilitate retention, participants will receive \$20 incentives after completing each survey (baseline, 3-, and 6-month follow-up), and the OC-HE will ask participants about how they are feeling about the program and what can be done to support their continued participation in the intervention at each follow-up encounters.

Participant Incentives

At the end of the baseline interview, participants will fill out the reimbursement form, which collects the participant's name, address, and citizenship status. At the end of the baseline, 3 month, and 6 month interviews, the research assistant will send the information to University of Iowa Shared Services, who will process a \$20 check to be sent to the address provided by the participant. The total compensation for the entire study is \$60 per participant. If the participant completes at least 51% of the interview questions, they will receive the \$20 compensation for that interview. To minimize coercion or undue influence, the level of incentive has been capped at \$20 per interview. All participants will be informed during the consent procedure that their participation in this study is completely voluntary, they can stop at any time, deciding not to participate will not impact the services they may receive at UIHC.

Correcting Retention Problems

If the study team encounters retention problems, the PI and Co-PI will meet with the DSMB, clinical staff, interventionist, and research team members to address retention issues. The National Institute on Aging provides recruitment and retention tips in its Recruitment and Retention Tips document, which will be revisited at that time.

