6.0 Informed Consent

Documents Provided Prior to Consent

- Flyer (*Appendix D*)
- Study Information Sheet (*Appendix E*)
- Consent Letter (*Appendix F*)

Consent Procedures and Documentation

About the study: To collect the information about the reach of our program, the research and clinical team will collect information about all potential participants' age, gender, race, physical disability status (collected by whether the person needs assistance with evacuation), rurality, whether the potential participant agreed to participate, and the reason for declining. The PWD who receives the Alzheimer's or related dementia diagnosis is not the participant in the study, but the PWD is welcome to be in the room while the study is discussed. The research team member will explain that the study consists of a baseline interview, randomization into intervention group or standard care group, completing the intervention (if randomized into the intervention group), and a 3 month, and 6 month interview. Those in the standard care group will complete the baseline, 3 month, and 6 month interview on the same schedule as the intervention group, and will have an option of receiving a call from an options counselor after the 6 month interview has been completed. This call from an options counselor is not the intervention being tested, but standard care participants will be connected to an options counselor who will do their own options counseling after the research is complete if the participants desire. The purpose of this protocol is to make sure that anyone who agrees to participate in this study has access to support regardless of their study group status.

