6.1 HIPAA Authorization

Because we have access to health data through the electronic medical record and because we are collecting some data through the electronic medical record (MoCA and use of medical services), all research team members have completed HIPAA training through the University of Iowa Hospitals and Clinics Human Resources.

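### As written, being unreachable for an intervention session can end study participation, so survey outcomes can be lost by a route that only the intervention arm has

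*Protocol*

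**What the plan says.** Protocol section 5.0, Participant Retention, gives a single rule for two callers. Research staff and the OC-HE interventionist "will make up to 3 phone calls, at least three days apart, leaving a message if possible to schedule each encounter". At the third call, whichever of them is calling tells the participant that they are "welcome to contact the research team if they would like to stay enrolled in the study". Then: "The participant will have up to 1 month to call back after the 3rd phone call before they are dropped from the study". The consequence is leaving the study, not leaving the intervention. Section 7.0 also calls an OC-HE session an encounter, so the rule covers sessions as well as surveys.

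The two arms share the survey schedule. Section 6.0 says that controls "will complete the baseline, 3 month, and 6 month interview on the same schedule as the intervention group", and their optional counsellor call comes only after the 6-month interview. The intervention arm has sessions in addition. Sections 2.0 and 7.0 of the protocol describe an initial session and five monthly calls (six in all); the SAP's account of the intervention describes an initial call and two monthly calls (three in all).

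Two passages might be read as protection. Section 5.0 states: "All participants will be asked to participate in a baseline survey and follow-up surveys at three and six months". Section 12.4 has weekly team meetings to track the process. Neither says that a person who cannot be reached for a session stays in survey follow-up.

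**The concern.** Caregiver burden is a primary outcome (protocol section 1.0) and comes from the surveys. If collecting it depends on answering intervention calls in one arm only, the participants with 6-month data are no longer comparable groups as randomised. The people lost through the extra route are those the interventionist could not reach but who would still have answered a survey. They may be more burdened than the rest or less, so the distortion could go either way.

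Section 5.0 plans for 25% attrition leaving 40 per group, which takes loss to be equal between arms. The SAP text gives no missing-data method and no analysis population, so nothing there deals with unequal loss.

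The concern does not extend to everything. Surveys completed before a drop are kept, and the use of medical services taken from the electronic record (section 6.1) need not be lost.

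**Working it through.** **The plan's own figures.** 106 × (1 − 0.25) = 79.5, which agrees with the stated 80 (40 per group). The 84% power for 4 points cannot be reproduced directly, because no SD, alpha or sidedness is given. Assuming a two-sample t-test, two-sided 0.05, 40 per group, 84% power implies SD = 5.98.

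**Which session rounds can cost a survey.** Section 2.0 places the first session early: "OC-HE will conduct initial assessment to determine educational needs within 2 weeks of" randomisation. Later sessions are monthly. Three calls at least three days apart take at least 6 days (about 0.2 month), followed by up to 1 month's grace. Assume that scheduling starts near the due date and that the full month is allowed. The first drop then takes effect between 0 + 0.2 + 1 = 1.2 and 0.5 + 0.2 + 1 = 1.7 months. Later ones fall at 2.2–2.7, 3.2–3.7, 4.2–4.7, 5.2–5.7 and 6.2–6.7 months.

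- 3-month survey: about two rounds can cost it, under either schedule.
- 6-month survey: up to three rounds (SAP) or about five (protocol; the sixth acts too late).

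**Illustration 1: total loss held at 25%, all of it through this rule.** Let q be the assumed risk of loss per survey round, rq the risk per session round, and s the number of session rounds that can act before the 6-month survey. Rounds are independent, with one scheduling round per session.

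- OC-HE 6-month loss = 1 − (1 − rq)^s (1 − q)²
- Control 6-month loss = 1 − (1 − q)²
- Solve for q so that the average of the two is 0.25.
- 3-month gap = [1 − (1 − rq)² (1 − q)] − q

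For s = 3, r = 1: q = 0.0810; 1 − 0.919⁵ = 34.5%; 1 − 0.919² = 15.5%; average 25%.

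| s | r | q | OC-HE loss | Control loss | 6-month gap (points) | 3-month gap (points) |
|---|---|---|---|---|---|---|
| 3 | 1 | 0.0810 | 34.5% | 15.5% | 18.9 | 14.3 |
| 3 | 0.5 | 0.1010 | 30.8% | 19.2% | 11.6 | 8.9 |
| 3 | 0.25 | 0.1152 | 28.3% | 21.7% | 6.6 | 5.0 |
| 5 | 1 | 0.0648 | 37.5% | 12.5% | 24.9 | 11.7 |
| 5 | 0.5 | 0.0872 | 33.3% | 16.7% | 16.6 | 7.8 |
| 5 | 0.25 | 0.1055 | 30.0% | 20.0% | 10.0 | 4.7 |

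Gaps are taken before rounding.

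**Effect on the burden contrast.** Suppose that dropped participants differ from those kept by D points on average, equally in both arms (assumption). Then the mean among those kept differs from the full-arm mean by loss × D, and the contrast between arms shifts by gap × D. For each 1 point of D the shift is 0.07–0.19 points (three rounds) or 0.10–0.25 (five), sign unknown.

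**Illustration 2: both arms lose 25% at survey rounds, and the session route adds to that.** Extra OC-HE completers lost = 53 × f × [1 − (1 − p)^s], where p is the drop risk per session round and f the share of those dropped at a session who would have answered the surveys. For p = 1%, s = 3, f = 0.75: 53 × 0.75 × (1 − 0.99³) = 1.2.

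| f | s | p = 1% | p = 2% | p = 5% |
|---|---|---|---|---|
| 0.75 | 3 | 1.2 | 2.3 | 5.7 |
| 0.75 | 5 | 1.9 | 3.8 | 9.0 |
| 0.25 | 3 | 0.4 | 0.8 | 1.9 |
| 0.25 | 5 | 0.6 | 1.3 | 3.0 |
| 0 | 3 or 5 | 0 | 0 | 0 |

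No controls are lost by this route.

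**Power, at SD 5.98.** Illustration 1 gives 82.7–83.7%. The lowest value in illustration 2 is 78.4% (s = 5, p = 5%, f = 0.75; 30.8 v 39.8 completers).

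**The case against.** The reading of the rule is hard to dispute; its weight is easier to dispute.

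- **Other documents.** The text is a manual of procedures. It cites a study protocol in an appendix, a data management plan and interventionist documentation that are not in the text available. One of these might separate stopping the intervention from leaving the study. That is fair, and it limits the finding to the text as written.
- **Oversight.** Section 5.0 provides for a meeting with the DSMB if retention is poor, section 15.0 has the DSMB review retention, and under section 10.0 the statistician alone prepares by-group reports. The interventionist also asks, at follow-up encounters, what would support continued participation. These could reveal or reduce unequal loss, but they exempt no one from the rule.
- **The illustrations are high.** Illustration 1 leaves no room for death, refusal or voluntary withdrawal. If 12.5% of each arm is lost for reasons unrelated to arm (assumption; both retention terms are multiplied by 0.875 and q re-solved to the same 25% total), the three-round gaps fall from 18.9, 11.6 and 6.6 points to 10.0, 6.3 and 3.6. With 19% they are 5.0, 3.1 and 1.8. This stands, and it is why the tables are upper-end figures.
- **Independence.** Someone who ignores three calls and a month's grace may well miss the survey too. This also stands: at f = 0 there is no extra loss.
- **Schedule.** If the SAP's three-session version is what was delivered, the five-round rows do not apply.
- **Small shift.** A shift of 0.07–0.25 points per point of D is small against a 4-point target, in a single-site Stage 1 study. It grows in proportion to D, however, and D is unknown.

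**Conclusion.** The concern holds. The written rule lets failure to reach someone for an intervention session end their survey follow-up, and only one arm has such sessions before the 6-month survey. This is a stated rule with an arm-specific consequence, not merely missing detail.

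The reading of the text is firm; the size is not. No per-round risk is given, the direction cannot be derived, and the effect could be near zero. With all attrition routed through the rule, and assumed risks and independence, the 6-month gap in loss is 6.6–18.9 points (SAP schedule) or 10.0–24.9 (protocol schedule); arm-neutral losses reduce it. Power is a side issue. Whether anyone was actually dropped this way is unknown. A correction is worth making because it is cheap and protects a primary outcome.

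**What to change.** **If follow-up has ended.** The planned dates suggest so: the protocol aimed to "complete recruitment by September, 2020, and complete data collection by March 2021", and the SAP is dated January 2022.

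- Report drops by arm and by the type of call that triggered them (OC-HE session or survey). If none were triggered by a session, say so; that settles the point.
- Analyse as randomised.
- Add one sensitivity analysis that shifts imputed burden upwards and downwards for those dropped at a session round.

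Cost: one table and one extra analysis. The SAP text contains no between-arm burden model or imputation model for this to attach to, so these must be specified too; the burden comparison is needed in any case for the primary objective.

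**If follow-up is open, or the manual is reused.** Change the retention rule in section 5.0 so that being unreachable for an OC-HE session is recorded as a missed session and does not end study participation. Attempt the 3- and 6-month surveys for everyone randomised who has not withdrawn from follow-up, with equal contact effort in both arms. Cost: one changed sentence, a few more survey calls by existing staff, and up to two $20 payments (at most $40) for each extra person followed.

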5.1 Screening and Eligibility Criteria

Assuming some people may not meet the inclusion criteria, we anticipate screening around 138 potential participants including women and minorities to reach target enrollment size.

Participants will be screened verbally, with the research assistant asking whether the participant meets the inclusion criteria (*see Eligibility Screening Tool in Appendix B*). Participants must meet *all* of the inclusion criteria in order to be eligible to participate in the study. Once the individual has been determined to be eligible, research assistant will schedule a time with the individual to consent to the study. After the individual has received the consent letter and the research assistant has read through the document with the individual, and the individual agrees to participate, the he/she will be considered enrolled. The participant will not be randomized until after completing the baseline survey. For every eligible potential participant, the research assistant will collect information about their age, gender, race, physical disability status

(whether the person needs assistance completing study-related tasks such as consenting and participating in interviews), whether the potential participant agreed to participate, and the reason for declining using the recruitment log. This will provide information on the extent to which our program is reaching caregivers of diverse backgrounds and to inform ways to increase reach to under-represented groups. Being included in the recruitment log does not indicate that the individual is necessarily enrolled in the study. Women and minority groups are encouraged to participate in this study. Because of the demographic characteristic of the patient population at the UIHC, primarily white, we will attempt to reach out to minority participants as much as we can to increase diversity. The control group will have the same inclusion/exclusion criteria.

One of the eligibility criteria, diagnosis of dementia, will be determined based on the clinical diagnosis made by physicians in our collaborating clinics. Once potential participants are identified by the clinical staff, research staff will conduct other assessments related to screening to determine eligibility using the above-described eligibility screening tool, before enrolling the participant. Screening and enrollment procedures will be conducted by one or two research staff to minimize variability. If more than one staff will engage in these procedures, two staff members will discuss procedures and criteria in detail to minimize variability in these procedures.

Individuals who exhibit high levels of anxiety based on the GAD-7 scale¹ (score of 10 or higher) in baseline will be advised to seek clinical care. These individuals will have an option to discontinue in this study.

5.2 Screening/Recruitment Log

An example of the recruitment log is provided in Appendix C of this document. The recruitment log will contain the participants' age, gender, race, physical disability status (collected by whether the person needs assistance with evacuation), rurality, whether the potential participant agreed to participate, and the reason for declining. This will give information on whether our program is reaching older adults from diverse backgrounds and to inform ways to increase reach to under-represented groups.

5.3 Eligibility Criteria

Inclusion Criteria

Family Participants/Caregivers

1. Over the age of 18
2. Self-reported family member/caregiver of someone who has been diagnosed with Alzheimer's/dementia within the past 6 months
3. Lives in the state of Iowa or the PWD lives in Iowa
4. No cognitive limitations that prevent them from consenting or participating in interviews (Evaluation to Sign an Informed Consent Document for Research, a form provided by the University of Iowa Institutional Review Board shown in Appendix E)
5. Access to necessary resources for participating in monthly phone calls

Staff participants

1. During the time of the study, worked as staff at the UIHC Neurology, Memory Disorder, or Psychiatry clinic and took a part in this study; or Served in an administrative role at the Heritage Area Agency on Aging during this project period or delivered intervention for this study
2. Over the age of 18

Exclusion criteria:

1. Those residing at care settings at the time of the recruitment
2. Families/caregivers of those diagnosed as predementia or mild cognitive impairment
3. Individuals with cognitive impairments and physical limitations that limit ability to make informed decisions or participate in interviews.

Individuals who exhibit high levels of anxiety based on the GAD-7 scale¹³ (score of 10 or higher) in baseline will be advised to seek clinical care. These individuals will have the option to discontinue in this study.

6.0 Informed Consent

Documents Provided Prior to Consent

- Flyer (*Appendix D*)
- Study Information Sheet (*Appendix E*)
- Consent Letter (*Appendix F*)

Consent Procedures and Documentation

About the study: To collect the information about the reach of our program, the research and clinical team will collect information about all potential participants' age, gender, race, physical disability status (collected by whether the person needs assistance with evacuation), rurality, whether the potential participant agreed to participate, and the reason for declining. The PWD who receives the Alzheimer's or related dementia diagnosis is not the participant in the study, but the PWD is welcome to be in the room while the study is discussed. The research team member will explain that the study consists of a baseline interview, randomization into intervention group or standard care group, completing the intervention (if randomized into the intervention group), and a 3 month, and 6 month interview. Those in the standard care group will complete the baseline, 3 month, and 6 month interview on the same schedule as the intervention group, and will have an option of receiving a call from an options counselor after the 6 month interview has been completed. This call from an options counselor is not the intervention being tested, but standard care participants will be connected to an options counselor who will do their own options counseling after the research is complete if the participants desire. The purpose of this protocol is to make sure that anyone who agrees to participate in this study has access to support regardless of their study group status.

While the potential participant wait as the PWD engages in various components of the clinical visit with various clinical care team members, research staff will explain the study, screen for eligibility, and invite one eligible family member who likely will coordinate care for the PWD to participate. If the potential participants agrees to participate in the study, he/she will be consented in the patient's examination room or in other private rooms (e.g., consultation room) using an informed consent letter. If the potential participant would like to think about whether he/she want to participate, the research team member will give the consent letter and ask for permission to share the potential participant's phone number with the research staff who would call them within a week if he/she does not call the research office first. Once the potential participant and research assistant have established contact, they will arrange a time to meet in person in a private location, or via telephone where the research assistant will read through the consent letter with the potential participant and consent them if they agree to participate.

To minimize the possibility of coercion, all participants will be informed during the consent procedure that their participation in this study is completely voluntary, they can stop at any time, deciding not to participate will not impact the services they receive at the UIHC.

Research Manager [name] and Student Interviewer [name] will discuss the nature of the study with potential participants. While consent letters do not need to be signed, [name] or [name] will explain the elements of consent to each potential participant before they complete the baseline interview. The participant will keep a copy of the consent letter and will be offered a new copy of the letter at the 3 month and 6 month follow up interviews.

